Appendix 3. van der Heijde modified Total Sharp Score (mTSS)

1) Definition of mTSS

The joint erosion score is a summary of erosion severity in 32 joints of the hands and 12 joints in the feet, as shown below for the joints assessed for erosions.

Hands/Fingers MCP: Metacarpophalangeal joints I – V (n = 10)	Hands/Wrist: Multangular bones (trapezium & trapezoid) (n = 2)
Hands/Fingers PIP: Proximal interphalangeal joints II – V (n = 8)	Hands/Wrist: Scaphoid(Navicular) bones (n = 2)
Hands/Fingers IP (thumbs): Interphalangeal joints (n = 2)	Hands/Wrist: Lunate bones (n=2)
Hands/Fingers (thumbs): Proximal Metacarpal joints (n = 2)	Feet/Toes MTP: Metatarsophalangeal joints I – V (n = 10)
Hands/Wrist: Distal Radius (n = 2)	Feet/Toes IP (big toes): Interphalangeal joints (n = 2)
Hands/Wrist: Distal Ulna (n = 2)	

An erosion score of 0 to 5 is given to each joint in the hands and wrists, and a score of 0 to 10 is given to each joint in the feet. Each hand and wrist joint is scored, according to the surface area involved, from 0 to 5, with 5 indicating extensive loss of bone from more than one half of the articulating bone (0 indicates no erosion). Because each side of a foot joint is graded on this scale, the maximum erosion score for a foot joint is 10. Thus, the maximal erosion score is $(32*5) + (12*10) = 280$. A joint may not be evaluable due to surgery (ie, joint replacement) or may be radiographically insufficient for reading.

The joint space narrowing (JSN) score summarizes the severity of JSN in 30 joints of the hands/wrists and 12 joints of the feet, as shown below for the joints assessed for JSN.

Hand/Fingers MCP: Metacarpophalangeal joints I – V (n = 10)	Hand/Wrist: Capitate-scaphoid Joint (n = 2)
Hand/Fingers PIP: Proximal interphalangeal joints II – V (n = 8)	Hand/Wrist: Scaphoid-radius Joint (n=2)
Hand/Fingers CMC: Carpometacarpal joints III, IV, V (n = 6)	Foot/Toes MTP: Metatarsophalangeal joints (n = 10)
Hand/Wrist: Scaphoid-Trapezium Joint (n = 2)	Foot/Toes IP: Interphalangeal joints (n = 2)

Assessment of JSN for each hand (15 joints per hand) and foot (6 joints per foot), including subluxation, is scored from 0 to 4, with 0 indicating normal or no narrowing and 4 indicating complete loss of joint space, bony ankylosis, or luxation. Thus, the maximal JSN score is $(30*4) + (12*4) = 168$. A joint may not be evaluable due to subluxation, luxations, surgery (ie, joint replacement) or may be radiographically insufficient for reading.

The mTSS is defined as the erosion score plus the joint space narrowing score.

The maximum scores (adding up both hands/wrists and feet) are:

Radiography	Maximum score of hands/wrists	Maximum score of feet	Maximum score (add up hands/ wrists and feet)
Erosion score	32 joints * 5 = 160	12 joints * 10 = 120	280
JSN score	30 joints * 4 = 120	12 joints * 4 = 48	168
mTSS	280	168	448

2) Handling of Missing Joint Data

This section is focused on how to handle missing scores for individual joints during mTSS derivation.

If repeated X-ray was taken at screening, Week 12, Week 24 or early termination visit, the joint scores from the repeated X-ray will be set to missing if (repeated X-ray date - original X-ray date) > 28 days. At Week 52 the joint scores from the repeat X-ray will be set to missing if (repeated X-ray date - original X-ray date) > 42 days. If a joint was identified as surgically modified at screening, this joint will be set to be missing at all following visits.

Step 1 is to identify missing joint scores and impute values when applicable for each reader. The joints are divided into 8 segments. A segment is adequate when the total number of joints with nonmissing score is above the threshold as defined in the table below.

The change score of missing joints within an segment will be imputed based on the mean change scores of the available joints of that segment. After the missing joint change scores are imputed, the sum of joint change scores will be computed for each segment.

Segment	Total number of joints	Adequacy threshold
PIP Erosion	8	5
MCP and Thumb Erosion	12	7
Wrist Erosion	12	7
Foot Erosion	12	7
PIP JSN	8	5
MCP and Thumb JSN	10	6
Wrist JSN	12	7
Foot JSN	12	7

Step 2 is to identify missing timepoint and impute values when applicable for each reader.

The mTSS at baseline will be set to missing if any of the segments is inadequate. The mTSS at postbaseline visits will be set to missing if more than 3 segments are inadequate; otherwise imputation will be applied to imputed segments. The change score of the missing segments at a timepoint will be imputed based on the mean change scores of the available segments of that timepoint.

The erosion score and JSN score at baseline will be set to missing if any of the segments that contribute to derive either the erosion score or JSN score is inadequate, respectively. The erosion score and JSN score at postbaseline visits will be set to missing if more than 1 segment is inadequate, respectively; otherwise the change score of the missing segment will be imputed in the similar way as mTSS.

The missing joint scores at baseline will be imputed when all of the segments at baseline are adequate and the corresponding joints are scored at Week 24. If the corresponding segment at Week 24 is also adequate, the missing joint change scores at Week 24 will be imputed first using the method described before, and the missing joint score at baseline will be imputed as joint score at Week 24 minus the change in joint score. The mTSS at baseline will be the sum of the scores after imputation. The mTSS at postbaseline visits will be derived as change in mTSS plus baseline mTSS. The erosion score and JSN score at baseline and postbaseline visits will be derived in the similar way as mTSS.

Step 3 is to identify which reader pair will be used to derive final mTSS, erosion score and JSN score when an adjudicated read is present. The selection is made at Week 24 based on changes in mTSS as specified below and will be applied to all the visits.

- If both readers and adjudicator have change in mTSS available, the selected reader will be the one whose change in mTSS is closest to that of adjudicator. If the differences of change in mTSS comparing to adjudicator are the same for both readers, then both readers will be selected.
- If adjudicator's change in mTSS is available, but one of the readers' change in mTSS is missing, then the other reader will be selected.

Step 4 is to derive the final mTSS and final change in mTSS at a given timepoint. In the case of not adjudicated subjects the final mTSS will be the mean of the mTSS generated by the 2 readers. For the final change in mTSS, the change from baseline in mTSS will first be calculated for the 2 readers separately, and the final change score will be the mean of these two change scores. In the case of adjudicated subjects the final mTSS and final change in mTSS will be the mean of the mTSS and change in mTSS generated by the selected reader(s) at step 3 and the adjudicator respectively. The final erosion score, JSN score, and change in erosion and JSN score will be derived in the similar way as mTSS.

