3.2. Study Design

This is a randomized, double-blind, placebo- and active-controlled, Phase 3 study in adult male and female subjects with active RA who have an inadequate response to MTX. The study is designed to evaluate the efficacy, safety and tolerability of filgotinib as well as its effect on patient-reported outcomes, including work productivity, fatigue, and quality of life. In addition, PK will be assessed.

Adult male and female subjects with active RA will be screened to determine eligibility as per the inclusion and exclusion criteria (see Section 4.2 and 4.3, respectively). The Screening period will be up to 28 days. The screening window may be extended to up to 42 days prior to the Day 1 visit for subjects who require repeat collection of radiographs.

Written informed consent must be obtained before any study-related procedures take place. During the Screening period, following signing of the informed consent form (ICF), radiographs (hands, wrists, and feet) will be sent for central review for confirmation of the number of documented joint erosions. Note that radiographs need to be sent for central review as soon as possible after capture and prior to Day 1 to allow for central reading and confirmation of the joint erosions for eligibility purposes.

Subjects will be randomized in a 3:3:2:3 ratio to filgotinib 200 mg, filgotinib 100 mg, active comparator (adalimumab), or matching placebo controls administered for up to 52 weeks in a double blind fashion.

At Week 14, subjects who have not achieved a 20% improvement from Day 1 in both swollen joint count (SJC) and tender joint count (TJC) will discontinue investigational therapy but will continue with study visits and assessments per protocol. All subjects who discontinue from investigational therapy, are to receive standard of care treatment for their RA as determined by the investigator. At Week 24 all subjects assigned to placebo + MTX will be reassigned 1:1 to either filgotinib 100 mg q.d. or 200 mg q.d. in addition to MTX in a blinded fashion and will continue the study through Week 52.

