3.8.2. Analysis Visit Windows

Subject visits may not occur on protocol-specified days. Therefore, for the purpose of analysis, observations will be assigned to analysis windows.

In general, the baseline value will be the last nonmissing value on or prior to the first dose date of study drug, except for the mTSS baseline value. The mTSS baseline value will be derived based on the measurements collected on or prior to the first dose date of study drug + 14 days given the potential delay in scheduling an x-ray assessment. If multiple valid, nonmissing measurements exist in the analysis window as aforementioned, in general, the last nonmissing mTSS value on or prior to the first dose date of study drug will be selected as the baseline value; If all these multiple measurements occur at post first dosing, the value closest to the first dose date will be selected as the baseline value.

For subjects who were on placebo and then re-randomized, the baseline after Week 24 will be the last nonmissing value obtained on or prior to the first dose date of filgotinib, except for the mTSS baseline value. The mTSS baseline value will be derived based on the measurements collected on or prior to the first dose date of filgotinib + 14 days given the potential delay in scheduling an x-ray assessment. If multiple valid, nonmissing measurements exist in the analysis window as aforementioned, in general, the last nonmissing mTSS value on or prior to the first dose date of filgotinib will be selected as the baseline value; If all these multiple measurements occur at post first dosing of filgotinib, the value closest to the first dose date of filgotinib will be selected as the baseline value.

For efficacy endpoints, vital signs, ECG, weight, lipids and safety laboratory data, the analysis visit windows will be applied to data collected during the ‘on-treatment’ period. The ‘on-treatment’ period is defined as the last dose date of any study drug + 7 days.

The analysis windows for on-treatment efficacy endpoints including joint count assessment, HAQ-DI (including subject’s pain assessment), subject’s global assessment (SGA), physician’s global assessment (PGA), serum CRP , exploratory patient reported outcome (PRO), and vital signs, weight, and safety laboratory data (lipid data excluded) are provided in [Table 3-1](#) and [Table 3-2](#).

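### The SAP's 28-day limit on repeat screening X-rays does not fit the protocol's 42-day screening extension for such repeats, so some subjects can needlessly lose their baseline mTSS

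*SAP*

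**What the plan says.** Three rules bear on the baseline film.

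- **Protocol 3.2, Study Design.** Screening normally lasts four weeks ("The Screening period will be up to 28 days"), with one exception: "The screening window may be extended to up to 42 days prior to the Day 1 visit for subjects who require repeat collection of radiographs".
- **SAP 3.8.2, Analysis Visit Windows.** Baseline mTSS is "derived based on the measurements collected on or prior to the first dose date of study drug + 14 days", to allow for late scheduling of X-rays. When several values qualify, the last nonmissing one on or before first dose is used.
- **SAP Appendix 3, handling of missing joint data.** For films repeated at screening, Week 12, Week 24 or early termination, "the joint scores from the repeated X-ray will be set to missing if (repeated X-ray date - original X-ray date) > 28 days". Week 52 has its own, longer limit of 42 days ("At Week 52 the joint scores from the repeat X-ray will be set to missing if" the gap exceeds that).

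Appendix 3 also treats baseline more strictly than later visits. "The mTSS at baseline will be set to missing if any of the segments is inadequate", whereas a post-baseline mTSS is set to missing only when more than three segments are inadequate. Missing baseline joints are imputed from Week 24 only when every baseline segment is already adequate.

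**The concern.** The protocol lengthens screening specifically so that radiographs can be retaken, but the scoring rule can discard the film that the extension was meant to obtain. The SAP neither reconciles the windows nor explains the 28 days, and in the same paragraph it tolerates 42 days at Week 52.

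The baseline film matters most because every change score depends on it. Under SAP 6.3.2 the mixed model needs a baseline and at least one post-baseline value. Under 6.3.3.2 the multiple-imputation and tipping-point analyses also start from subjects with a baseline measurement. A subject without baseline mTSS is therefore absent from hypotheses 6 and 7 of the testing hierarchy, and no planned sensitivity analysis brings that subject back. The Week 24 mTSS comparison is also the one that set the sample size.

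**Working it through.** **1. The plan's own figure.** Inputs from SAP 1.3: difference 0.4, SD 1.85, two-sided 0.05, 90% power.

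n per group = 2 × (1.960 + 1.282)² × 1.85² / 0.4² ≈ 449.5, rounded up to 450. Power at 450 = Φ(0.4 / (1.85 × √(2/450)) − 1.960) = Φ(3.243 − 1.960) = 90.0%. The stated figure reproduces, and the calculation shows no allowance for missing films.

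**2. Which repeats are discarded.** Let the original film be d days and the repeat r days before Day 1. The gap is d − r, and the repeat is discarded if d − r > 28.

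- Ordinary screening (d ≤ 28): a repeat by Day 1 has a gap of at most 28 days and is always kept.
- Extended screening (d ≤ 42): discarding requires d ≥ 29 and r ≤ d − 29, so r is at most 13. An original on Day -42 with a repeat on Day -14 (gap 28) is kept; with a repeat on Day -13 (gap 29) it is not.
- Example: Day -40 and Day -5 give a gap of 35 days. The later film is discarded although it is the closer one to Day 1.
- Largest gap: 42 days at Day 1, or 42 + 14 = 56 days at the end of the SAP baseline window.

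Before dosing, then, the conflict arises only for subjects given the extension, and only when an early original is followed by a late repeat.

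**3. When the discard costs the baseline.** Only the repeat's scores are removed, so the original film must stand alone. Joint totals and thresholds are from Appendix 3. The remaining joints assume that one whole side is unreadable on the original.

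| Segment | Joints left / total | Threshold |
|---|---|---|
| PIP erosion, PIP JSN | 4 / 8 | 5 |
| MCP and thumb erosion | 6 / 12 | 7 |
| MCP and thumb JSN | 5 / 10 | 6 |
| Wrist erosion, wrist JSN | 6 / 12 | 7 |
| Foot erosion, foot JSN | 6 / 12 | 7 |

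Any one unreadable hand or foot makes a segment inadequate and sets baseline mTSS to missing. The imputation from Week 24 cannot help, because it requires all baseline segments to be adequate. If instead no more than 3 of 8, 4 of 10 or 5 of 12 joints in a segment are unreadable (one fewer if the threshold must be strictly exceeded), the segment stays adequate and the baseline survives.

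**4. Size.** The documents give no repeat rate. Assume that 5% to 10% of subjects need a repeat baseline view, and that 10% to 30% of those lose their baseline through the limit. The loss is then 0.05 × 0.10 = 0.5% to 0.10 × 0.30 = 3%, or about 2 to 14 of 450 per arm.

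| Loss per arm | n | Power |
|---|---|---|
| 0% | 450 | 90.0% |
| 0.5% | 447.75 | 89.9% |
| 1% | 445.5 | 89.7% |
| 3% | 436.5 | 89.1% |

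**The case against.** The strongest defence is that the rules measure different intervals. The 42 days run from screening to Day 1, and the 28 days run from film to film, so most repeats in the extended window are kept. Protocol 3.2 also asks for films to be sent promptly for central reading before Day 1, which discourages very late repeats where eligibility rests on erosions. This narrows the affected group but does not empty it. Inclusion criterion 4c admits subjects on CRP alone, so an unscorable view need not prevent randomization.

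A sponsor could add that a longer tolerance at Week 52 does not prove 28 days wrong at baseline, which is the reference for every change score. That is fair, but the SAP gives no such reason.

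Three stronger readings are tempting, and the documents do not support them.

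- A reader might infer that every subject with a late repeat loses baseline mTSS. The original's scores remain, and the baseline is lost only if that film alone leaves an inadequate segment. The documents do not say why films are repeated, or that a whole hand or foot is typically lost.
- A reader might infer that the protocol permits gaps of 56 days. The 14 days after first dose are an analysis tolerance. The procedures table schedules the baseline film at Screening and no repeat after dosing.
- A reader might infer bias between arms. In the Day -40 and Day -5 example both film dates precede randomization, so the discard cannot depend on the arm.

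**Conclusion.** The inconsistency is real and its reach is limited. The 28-day rule can discard a repeat film taken inside both the protocol's extended screening window and the SAP's baseline window. A subject so affected can lose baseline mTSS, on condition that the original film leaves at least one segment inadequate.

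On the assumed loss of 0.5% to 3% per arm, the cost is under one percentage point of power. That range has no source in the documents; only the subject-level film dates would show the true number. The point is avoidable loss of data on a key secondary endpoint, worth correcting because the correction is cheap. It does not call the radiographic comparison into question.

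**What to change.** In SAP Appendix 3, for screening films only, change the limit from 28 to 42 days. A repeat taken by Day 1 within the extended window is at most 42 days after the original, so none would be discarded. The limit would also equal the one already used at Week 52. Leave the limits for Week 12, Week 24 and early termination as they are. If 28 days at screening is deliberate, give the reason instead.

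Because the SAP does not say how original and repeat scores are combined, a sentence on that and a count of affected subjects by arm would be useful additions.

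The cost is one line of SAP text. The downside is that a few baselines may use views up to six weeks apart. Films repeated after first dose with a gap above 42 days would still be discarded, which is acceptable because the protocol schedules none.

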Appendix 4. Treatment Satisfaction Questionnaire for Medication (TSQM)

TSQM scale scores are computed by adding the items loading on each factor. The lowest possible score is subtracted from this composite score and divided by the greatest possible score minus the lowest possible score. This provides a transformed score between 0 and 1 that should be multiplied by 100. Note that only one item may be missing from each scale before the subscale should be considered invalid for that respondent.

EFFECTIVENESS:

$([\text{Sum}(\text{Item 1} + \text{Item 2} + \text{Item 3}) - 3] \text{ divided by } 18) * 100$

If one item is missing

$([\text{Sum}(\text{Item 1} + \text{Item 2} + \text{Item 3}) - 2] \text{ divided by } 12) * 100$

SIDE EFFECTS:

If Question 4 is answered 'No', then score = 100

Else,

$([\text{Sum}(\text{Item 5 to Item 8}) - 4] \text{ divided by } 16) * 100$

If one item is missing

$([\text{Sum}(\text{Item 5 to Item 8}) - 3] \text{ divided by } 12) * 100$

CONVENIENCE:

$([\text{Sum}(\text{Item 9 to Item 11}) - 3] \text{ divided by } 18) * 100$

If one item is missing

$([\text{Sum}(\text{Item 9 to Item 11}) - 2] \text{ divided by } 12) * 100$

GLOBAL SATISFACTION:

$([\text{Sum}(\text{Item 12 to Item 14}) - 3] \text{ divided by } 14) * 100$

If either Item 12 or 13 is missing

$([\text{Sum}(\text{Item 12 to Item 14}) - 2] \text{ divided by } 10) * 100$

If Item 14 is missing

$([\text{Sum}(\text{Item 12 and Item 13}) - 2] \text{ divided by } 8) * 100$

Appendix 5. Corticosteroids

The following table will be used for converting non-prednisone medications to prednisone equivalent:

*Example: Subject is taking 8 mg of Methylprednisolone orally daily. To get the equivalent dose of prednisone: 8 mg Methylprednisolone = $(5*8)/4 = 10$ mg prednisone.*

Corticosteroids Name	Equivalent Dose (mg) to 5 mg Prednisone
Betamethasone	0.75
Betamethasone Dipropionate	0.75
Betamethasone Sodium Phosphate	0.75
Cortisone	20
Dexamethasone	0.75
Dexamethasone Palmitate	0.75
Dexamethasone Phosphate	0.75
Dexamethasone Sodium Phosphate	0.75
Hydrocortisone	20
Meprednisone	4
Methylprednisolone	4
Methylprednisolone Acetate	4
Methylprednisolone Sodium Succinate	4
Prednisone	5
Prednisolone	5
Prednisolone Farnesylate	5
Prednisolone Sodium Succinate	5
Triamcinolone	4

Appendix 6. SAS Programming for Tipping Point Analysis for Binary Endpoint

The following **%tp_binary** macro generates multiple imputed data and a set of the shift parameters that adjust the imputed values will be examined.

```

/*-----*/
/*--- Delta-Adjusting Method for Tipping Point Analysis for Binary Endpoint ---*/
/*---
/*--- Generate imputed data set for specified shift parameters ---*/
/*--- data= input data set ---*/
/*--- smin= min shift parameter for active drug ---*/
/*--- smax= max shift parameter for active drug ---*/
/*--- sinc= increment of the shift parameter for active drug ---*/
/*--- pmin= min shift parameter for placebo drug ---*/
/*--- pmax= max shift parameter for placebo drug ---*/
/*--- pinc= increment of the shift parameter for placebo drug ---*/
/*--- trt= treatment group indicator ---*/
/*--- out= output imputed data set ---*/
/*-----*/

%macro tp_binary( data=, smin=, smax=, sinc=, pmin=, pmax=, pinc=, trt=, out=);
  data &out;
  set _null_;
  run;

  /*----- # of shift values -----*/
  %let ncase_pbo = %sysevalf( (&pmax-&pmin)/&pinc, ceil );

  %do pc=0 %to &ncase_pbo;

  %let pj= %sysevalf( &pmin + &pc * &pinc);

  /*----- # of shift values -----*/
  %let ncase= %sysevalf( (&smax-&smin)/&sinc, ceil );

  /*----- Imputed data for each shift -----*/
  %do jc=0 %to &ncase;

  %let sj= %sysevalf( &smin + &jc * &sinc);

  proc mi data=&data seed=14823 nimpute=20 out=outmi;
    var trt01pn strat1V strat2V strat3V ACR20;
    class trt01pn strat1V strat2V strat3V ACR20;
    monotone logistic (ACR20 / link=glogit);
    mnar adjust(ACR20 (event='1') / adjustobs=(trt01pn="&trt") shift= &sj)
      adjust(ACR20 (event='1') / adjustobs=(trt01pn='3') shift= &pj);
  run;

  data outmi;
    set outmi;
    Shift_Trt= &sj;
    Shift_Pbo= &pj;
  run;

  data &out;

```

```
        set &out outmi;  
        run;  
  
    %end;  
%end;  
%mend tp_binary;
```

Appendix 7. SAS Programming for Tipping Point Analysis for Continuous Endpoint

The following **%tp_conti** macro generates multiple imputed data sets and a set of the shift parameters that adjust the imputed values will be examined.

```

/*****
/*--- Modified Tipping Point Analysis from Yuan's method ---*/
/*---
/*--- Generate imputed data set for specified shift parameters ---*/
/*--- data= input data set ---*/
/*--- smin= min shift parameter for active drug ---*/
/*--- smax= max shift parameter for active drug ---*/
/*--- sinc= increment of the shift parameter for active drug ---*/
/*--- pmin= min shift parameter for placebo drug ---*/
/*--- pmax= max shift parameter for placebo drug ---*/
/*--- pinc= increment of the shift parameter for placebo drug ---*/
/*--- trt= treatment group indicator (eg, 1= filgotinib 200 mg) ---*/
/*--- out= output imputed data set ---*/
*****/

```

```

%macro tp_conti( data=, smin=, smax=, sinc=, pmin=, pmax=, pinc=, trt=, out=);
  data &out;
  set _null_;
  run;

```

```

  %let ncase_pbo = %sysevalf( (&pmax-&pmin)/&pinc, ceil );

```

```

  %do pc=0 %to &ncase_pbo;

```

```

    %let pj= %sysevalf( &pmin + &pc * &pinc);

```

```

    /*----- # of shift values -----*/
    %let ncase= %sysevalf( (&smax-&smin)/&sinc, ceil );

```

```

    /*----- Imputed data for each shift -----*/
    %do jc=0 %to &ncase;

```

```

      %let sj= %sysevalf( &smin + &jc * &sinc);

```

```

      proc mi data=&data out=all_mono nimpute=20 seed=123;
        var v_1 v_2 v_3 v_4 v_5 v_6 v_7 v_8 v_9;
        mcmc chain=multiple impute=monotone;
      run;

```

```

      proc sort data=all_mono; by _Imputation_ trt01pn; run;

```

```

      proc mi data=all_mono out=outmi seed=465 nimpute=1;
        by _Imputation_ ;
        var trt01pn strat1V strat2V strat3V v_1 v_2 v_3 v_4 v_5 v_6 v_7 v_8 v_9;
        class trt01pn strat1V strat2V strat3V;
        monotone regression;
        mnar adjust( v_5 / adjustobs=(trt01pn="&trt") shift=&sj)
              adjust( v_5 / adjustobs=(trt01pn='3') shift= &pj);

```

```
run;

data outmi;
    set outmi;
    Shift_Trt= &sj;
    Shift_Pbo= &pj;
run;

data &out;
    set &out outmi;
run;
%end;
%mend tp_conti;
```

